12.2.4 Quality Assurance

The sponsor is implementing and maintaining quality assurance (QA) and quality control (QC) systems with written SOPs to ensure that studies are conducted and data are generated, documented, recorded and reported in compliance with the protocol, GCP and applicable regulatory requirement(s). Where applicable, the QA and QC systems and written SOPs of the CRO will be applied.

The sponsor or sponsor's designee may arrange to audit the study at any or all study sites and facilities. The audit may include on-site review of regulatory documents, CRFs and source documents. Direct access to these documents will be required by the auditors.

To support quality around subject safety and reliability of study results, quality tolerance limits (QTLs) are defined and monitored. QTLs represent the acceptable variation of study data, taking into consideration the current state of medical and statistical knowledge about the variables to be analyzed as well as the statistical design of the study. It is a level, point, or value associated with a parameter that should trigger an evaluation if a deviation is detected to determine if there is a possible systematic issue (i.e., a trend has occurred). The QTLs defined for this study, information regarding the QTL limit and limit justification, as well as associated activities are documented in STL-3458 QTL monitoring plan.

12.3 List of Excluded Concomitant Medications

These lists are not inclusive of all possible prohibited medications. In case of doubt, the Investigator must contact the local medical monitor.

- Use of hormonal medications such as hormone therapy, HRT or hormonal contraception or any treatment for menopausal symptoms (prescription, over the counter or herbal) is not allowed during the study.
- Investigational research products that have not been approved for any indication in the country where the subject is enrolled.

Strong CYP1A2 Inhibitors (AUCr > 5)	
Inhibitor	Therapeutic Class
Angelica root - Bai Zhi (Angelica dahurica radix)	Herbal Medications
ciprofloxacin	Antibiotics
clinafloxacin	Antibiotics
enoxacin	Antibiotics
fluvoxamine	SSRIs
oltipraz	Cancer Chemopreventive Agents
rofecoxib	NSAIDS
zafirlukast	Antiasthmatics
Moderate CYP1A2 Inhibitors (AUCr ≥ 2 and AUCr ≤ 5)	
Inhibitor	Therapeutic Class
MDMA	Recreational Drugs
etintidine	H-2 Receptor Antagonists
genistein	Food Products
idrocilamide	Muscle Relaxants
methoxsalen (8-methoxypsoralen)	Antipsoriatics
mexiletine	Antiarrhythmics
osilodrostat	Adrenal Steroidogenesis Inhibitors
oral contraceptives	Oral Contraceptives
phenylpropanolamine	Vasoconstrictors
pipemidic acid	Antibiotics
propafenone	Antiarrhythmics
propranolol	Alpha/Beta Adrenergic Antagonists
troleandomycin	Antibiotics
vemurafenib	Kinase Inhibitors

AUCr: area under the concentration-time curve ratio; CYP: cytochrome P450; MDMA: 3,4-methylenedioxymethamphetamine; NSAID: nonsteroidal anti-inflammatory drugs; SSRI: Selective serotonin reuptake inhibitors

Estrogen-Only Medicines	
Brand Name	Generic Name
Alora	Estradiol
Cenestin	Synthetic Conjugated Estrogens
Climara	Estradiol
Delestrogen	Estradiol Valerate
Divigel	Estradiol
Elestrin	Estradiol
Enjuvia	Synthetic Conjugated Estrogens
Esclim	Estradiol
Estrace	Estradiol
Estraderm	Estradiol
Estrasorb	Estradiol
Estring	Estradiol
EstroGel	Estradiol
Evamist	Estradiol
Femring	Estradiol Acetate
Femtrace	Estradiol Acetate
Menest	Esterified Estrogen
Menostar (only used to prevent osteoporosis)	Estradiol
Minivelle	Estradiol
Ogen	Estropipate
Ortho-Est	Estropipate
Premarin	Conjugated Estrogens
Vagifem	Estradiol
Vivelle	Estradiol
Vivelle-Dot	Estradiol
Table continued on next page	

Progestin-Only Medicines	
Brand Name	Generic Name
Prometrium	Micronized Progesterone
Aygestin	Norethindrone acetate
Provera	Medroxyprogesterone Acetate
Combination Estrogen and Progestin Medicines	
Brand Name	Generic Name
Activella	Estradiol/
	Norethindrone Acetate
Angeliq	Estradiol/Drospirenone
Climara Pro	Estradiol/
	Levonorgestrel
Combipatch	Estradiol/
	Norethindrone Acetate
Jinteli	Ethinyl Estradiol/
	Norethindrone Acetate
Mimvey	Estradiol/
	Norethindrone Acetate
Femhrt	Norethindrone Acetate/
	Ethinyl Estradiol
Prefest	Estradiol/
	Norgestimate
Prempro	Conjugated Estrogen/
	Medroxyprogesterone
Premphase	Conjugated Estrogen/
	Medroxyprogesterone
Combination Estrogen and Hormone Medicines	
Brand Name	Generic Name
Duavee	Conjugated Estrogen/ Bazedoxifene

12.4 Liver Safety Monitoring and Assessment

Any subject enrolled in a clinical study with active drug therapy and reveals an increase of serum aminotransferases (AT) to $> 3 \times \text{ULN}$ or bilirubin $> 2 \times \text{ULN}$ should undergo detailed testing for liver enzymes (including at least ALT, AST, ALP and TBL). Testing should be repeated within 72 hours of notification of the test results. For studies for which a central laboratory is used, alerts will be generated by the central laboratory regarding moderate and severe liver abnormality to inform the investigator and study team. Subjects should be asked if they have any symptoms suggestive of hepatobiliary dysfunction.

Definition of Liver Abnormalities

Confirmed abnormalities will be characterized as moderate and severe where ULN:

	ALT or AST		TBL
Moderate	$> 3 \times \text{ULN}$	or	$> 2 \times \text{ULN}$
Severe	$> 3 \times \text{ULN}$	and	$> 2 \times \text{ULN}$

In addition, the subject should be considered to have severe hepatic test abnormalities for any of the following:

- ALT or AST $> 8 \times \text{ULN}$
- ALT or AST $> 5 \times \text{ULN}$ for more than 2 weeks
- ALT or AST $> 3 \times \text{ULN}$ **AND** TBL $> 2 \times \text{ULN}$ or INR > 1.5 , or
- ALT or AST $> 3 \times \text{ULN}$ with the appearance of fatigue, nausea, vomiting, right upper quadrant pain or tenderness, fever, rash and/or eosinophilia ($> 5\%$ increase above baseline)

The investigator may determine that abnormal liver test results, other than as described above, may qualify as moderate or severe abnormalities and require additional monitoring and follow-up.

Follow-up Procedures

Confirmed moderate and severe abnormalities in hepatic tests should be thoroughly characterized by obtaining appropriate expert consultations, detailed pertinent history, physical examination and laboratory tests. The site staff is to complete the liver abnormality case report form (LA-CRF). Subjects with confirmed liver aminotransferases (ALT or AST) elevations should be followed as described below.

Moderate liver test abnormalities as defined above should be repeated 2 to 3 times weekly, and then weekly or less if abnormalities stabilize or the study drug has been discontinued and the subject is asymptomatic.

Severe liver test abnormalities as defined above, in the absence of another etiology, are considered an important medical event and should be reported as a SAE. The sponsor should be contacted and informed immediately of all subjects for whom severe hepatic liver function abnormalities possibly attributable to study drug are observed.

To further assess abnormal hepatic laboratory findings, the investigator is expected to:

- Obtain a more detailed history of symptoms and prior or concurrent diseases. Symptoms and new-onset diseases is to be recorded as “AEs” within the eCRF. Illnesses and conditions such as hypotensive events, and decompensated cardiac disease that may lead to secondary liver abnormalities should be noted. Nonalcoholic steatohepatitis is seen in obese hyperlipoproteinemic and/or diabetic patients, and may be associated with fluctuating AT levels. The investigator should ensure that the medical history form captures any illness that predates study enrollment that may be relevant in assessing hepatic function.
- Obtain a history of concomitant drug use (including nonprescription medication, complementary and alternative medications), alcohol use, recreational drug use and special diets. Medications, is to be entered in the eCRF. Information on alcohol, other substance use and diet should be entered on the LA-CRF or an appropriate document.
- Obtain a history of exposure to environmental chemical agents.
- Based on the subject’s history, other testing may be appropriate including:
 - Acute viral hepatitis (A, B, C, D, E or other infectious agents),
 - Ultrasound or other imaging to assess biliary tract disease,
 - Other laboratory tests including INR, direct bilirubin.
- Consider gastroenterology or hepatology consultations.
- Submit results for any additional testing and possible etiology on the LA-CRF or an appropriate document.

Study Treatment Discontinuation

In the absence of an explanation for increased liver aminotransferase (ALT or AST) tests, such as viral hepatitis, preexisting or acute liver disease or exposure to other agents associated with liver injury, the subject may be discontinued from study treatment. The investigator may determine that it is not in the subject’s best interest to continue study treatment. Study treatment must be discontinued and event be reported as an SAE if:

- ALT or AST $> 8 \times$ ULN
- ALT or AST $> 5 \times$ ULN for more than 2 weeks
- ALT or AST $> 3 \times$ ULN and TBL $> 2 \times$ ULN or INR > 1.5
- ALT or AST $> 3 \times$ ULN with the appearance of fatigue, nausea, vomiting, right upper quadrant pain or tenderness, fever, rash and/or eosinophilia ($> 5\%$ increase above baseline)

Subjects who develop a signal of liver injury will be monitored every 2 to 4 weeks if the study drug is discontinued. If the subject remains on study drug, they will be closely monitored for liver biochemistry results. Subjects with a signal of elevated transaminases ($> 3 \times$ ULN) will have a pre-dose PK sample drawn in addition to repeat blood draws for liver biochemistry monitoring. These samples can be held for potential analysis based on the subject’s clinical outcome.

In addition, if close monitoring for a subject with moderate or severe hepatic laboratory tests is not possible, study treatment should be discontinued.

*Hy's Law Definition: Drug-induced jaundice caused by hepatocellular injury, without a significant obstructive component, has a high rate of bad outcomes, from 10 to 50% mortality (or transplant).

The 2 "requirements" for Hy's Law are:

1. Evidence that a drug can cause hepatocellular-type injury, generally shown by an increase in transaminase elevations higher $3 \times \text{ULN}$ (" $2 \times \text{ULN}$ elevations are too common in treated and untreated patients to be discriminating").
2. Cases of increased bilirubin (at least $2 \times \text{ULN}$) with concurrent transaminase elevations at least $3 \times \text{ULN}$ and no evidence of intra- or extra-hepatic bilirubin obstruction (elevated ALP) or Gilbert's syndrome [Temple, 2006].

FDA Guidance for Industry, "Drug-Induced Liver Injury: Premarketing Clinical Evaluation," 2009:

1. The drug causes hepatocellular injury, generally shown by a higher incidence of 3-fold or greater elevations above the ULN of ALT or AST than the (nonhepatotoxic) control drug or placebo.
2. Among study subjects showing such AT elevations, often with ATs much greater than $3 \times \text{ULN}$, 1 or more also show elevation of serum TBL to $> 2 \times \text{ULN}$, without initial findings of cholestasis (elevated serum ALP).
3. No other reason can be found to explain the combination of increased AT and TBL, such as viral hepatitis A, B or C; preexisting or acute liver disease; or another drug capable of causing the observed injury.

References

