1.5 Risk Benefit Assessment

Fezolinetant is currently being developed for the treatment of VMS associated with the menopause (MR-VMS).

Based on recent advances in science, as well as the clinical data derived from 2 phase 2 clinical studies in women with VMS associated with the menopause, there are positive reasons to believe that fezolinetant can be an effective treatment for MR-VMS.

When given to normally cycling healthy women, fezolinetant is capable of altering the menstrual cycle and decreasing the circulating levels of E2, LH, progesterone (P4) and testosterone. Since this study aims to include menopausal women, these effects will be of less importance because of the physiological changes that happen in the climacterium (anovulation with loss of P4 and E2 production, and consequently increase of LH/FSH).

In terms of hormonal changes, a mild to moderate decrease of the already elevated LH and FSH plasma levels is anticipated. There are no known risks associated with this decrease of the gonadotropins in menopausal women.

Treatment with fezolinetant can cause adverse effects or other symptoms. Adverse effects that can be expected are those AEs that presented in fezolinetant clinical studies in healthy male and female volunteers, as well as in menopausal women.

Details of the AE profile from the completed clinical studies are presented in [Section 1.3 Fezolinetant Nonclinical and Clinical Data].

Across the completed phase 1 and 2a studies, there have been a small number of mild, transitory transaminase elevations observed both in patients/subjects who received either fezolinetant or placebo. There were no incidences of raised TBL and none of the patients/subjects experienced associated symptoms. In the recently completed phase 2b study ESN364_HF_205, transitory increases in transaminase enzymes, ALT/AST, have been reported in 7 subjects between 4 and 8 weeks after start of study treatment and in 2 unique subjects during study follow-up. Subjects were asymptomatic throughout and there was no evidence of functional liver impairment. Although there were cases with evidence of significant underlying hepatic conditions and other confounding factors, independent expert review concluded that the study drug was probably the cause of the increased transaminase levels. In all cases, transaminase enzyme levels rapidly decreased, in 2 cases during continuing treatment with study medication.

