5.5.1.2 Potential Cases of Drug-induced Liver Injury

Refer to [Appendix 12.4 Liver Safety Monitoring and Assessment] for detailed instructions on DILI. Abnormal values in AST and/or ALT concurrent or with abnormal elevations in TBL that meet the criteria outlined in [Appendix 12.4 Liver Safety Monitoring and Assessment], in the absence of other causes of liver injury, are considered potential cases of DILI (potential Hy's Law cases). Any subject discontinuations due to liver safety are always

to be considered important medical events and reported per [Section 5.5.5 Reporting of Serious Adverse Events].

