5.5.2 Definition of Serious Adverse Events

An AE is considered “serious” if, in the view of either the investigator or sponsor, it results in any of the following outcomes:

- Results in death
- Is life-threatening (an AE is considered “life-threatening” if, in the view of either the investigator or sponsor, its occurrence places the subject at immediate risk of death. It does not include an AE that, had it occurred in a more severe form, might have caused death)
- Results in persistent or significant disability/incapacity or substantial disruption of the ability to conduct normal life functions
- Results in congenital anomaly or birth defect
- Requires inpatient hospitalization (except for planned procedures as allowed per study) or leads to prolongation of hospitalization (except if prolongation of planned hospitalization is not caused by an AE). Hospitalization for treatment/observation/examination caused by AE is to be considered as serious.)
- Discontinuation due to increases in liver enzymes (Section 6.1)
- Other medically important events (defined in paragraph below)

Medical and scientific judgment should be exercised in deciding whether expedited reporting is appropriate in other situations, such as important medical events that may not be immediately life-threatening or result in death or hospitalization but may jeopardize the subject or may require intervention to prevent 1 of the other outcomes listed in the definition above. These events, including those that may result in disability/incapacity, usually are considered serious. Examples of such events are intensive treatment in an emergency room or at home for allergic bronchospasm; blood dyscrasias or convulsions that do not result in hospitalization; or development of drug dependency or drug abuse.

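### Appendix 12.4 gives two SAE reporting rules for the same four severe liver criteria, one conditional on cause and one not, and nothing says which governs

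*Protocol*

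**What the plan says.** All of the text below is current protocol text, not the amendment summary.

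- **Appendix 12.4, Definition of Liver Abnormalities.** After a short table, the appendix states that "the subject should be considered to have severe hepatic test abnormalities for any of the following" and gives four criteria: ALT or AST > 8 × ULN; > 5 × ULN for more than 2 weeks; > 3 × ULN with TBL > 2 × ULN or INR > 1.5; and > 3 × ULN with listed symptoms or eosinophilia. Investigators may also designate other results as moderate or severe.
- **Appendix 12.4, Follow-up Procedures.** Severe abnormalities, "in the absence of another etiology, are considered an important medical event and should be reported as a SAE". The next sentence asks for immediate sponsor contact for severe abnormalities that may be related to study drug.
- **Appendix 12.4, Study Treatment Discontinuation.** Where raised aminotransferases have no explanation, "the subject may be discontinued from study treatment". A separate sentence follows: "Study treatment must be discontinued and event be reported as an SAE if" any of the same four criteria is met. It has no condition on cause.
- **Section 6.1.** The same hepatic criteria are reasons for mandatory discontinuation. Three of the four need confirmation within 72 hours; none depends on cause.
- **Section 5.5.1.2.** "Any subject discontinuations due to liver safety are always" "to be considered important medical events and reported per [Section 5.5.5 Reporting of Serious Adverse Events".
- **Section 5.5.2.** "Discontinuation due to increases in liver enzymes (Section 6.1" is itself a seriousness criterion.
- **Section 5.5.5.** Any SAE goes to the sponsor within 24 hours of awareness.
- **12-week and 52-week SAPs, Section 6.5.1.** Serious TEAEs are counted by treatment group. Neither SAP has a rule that would settle the conflict.

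**The concern.** Whether an event is serious and whether the drug caused it are separate judgements in this protocol: Section 5.5.3 has the investigator answer a yes/no causality question for each event. The Follow-up sentence brings cause into the decision to report an SAE at all. Elsewhere the protocol ties the exclusion of other causes to the label of potential DILI or Hy's Law (Section 5.5.1.2 and the end of Appendix 12.4), not to seriousness.

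Liver injury is an important potential risk in Section 1.5. The same section reports that some phase 2b transaminase cases had underlying hepatic disease or other confounders, and that "independent expert review concluded that the study drug was probably the cause of the increased transaminase levels". A case with a competing explanation is the kind that the conditional sentence could lead a site not to report as an SAE. At stake is whether like cases are reported alike across sites, in SAE and expedited reporting (Section 5.5.5) and in the serious TEAE tables.

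**Working it through.** No sample size, power or event figure of the plan is involved, so there is nothing to reproduce. The check compares what triggers an SAE in each place.

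| Place | Trigger | Depends on cause? |
|---|---|---|
| 12.4, Follow-up Procedures | Severe abnormality | Yes |
| 12.4, Study Treatment Discontinuation | Any of the four criteria | No |
| 5.5.1.2 | Discontinuation for liver safety | No |
| 5.5.2 | Discontinuation for raised liver enzymes | No |

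**Step 1. Are the criteria the same?** Yes. The four items in the severe list and in the stop list match one for one. The severe row of the table (> 3 × ULN with TBL > 2 × ULN) falls within the third item.

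**Step 2. Does the reference to a missing explanation in the discontinuation paragraph carry over to the stop list?** No. It belongs to the permissive sentence ("the subject may be discontinued from study treatment"). The mandatory sentence stands by itself.

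**Step 3. Do Sections 5.5.1.2 and 5.5.2 contradict the Follow-up sentence directly?** No. Both are triggered by discontinuation, not by the laboratory result. They reach every severe on-treatment case only because Section 6.1 and the stop list make discontinuation mandatory for the same criteria. A severe value first seen after the last dose is outside both. The direct conflict is therefore between the two sentences of Appendix 12.4.

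**Step 4. A test case.** A woman on treatment has confirmed ALT > 8 × ULN, and the work-up shows acute viral hepatitis. The Follow-up sentence does not call for an SAE. The stop list does. So do Section 6.1 with 5.5.1.2, and Section 6.1 with 5.5.2.

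**Step 5. Effect on counts.** Let k be the number of severe events and s the share with another identified cause. The SAE count is k under the unconditional text and k(1 − s) under the conditional text, a difference of ks. The documents give no value for s. Over its full range of 0 to 1, the conditional count runs from k down to 0, so the formula shows the direction and no more.

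**Step 6. Which outputs use the SAE flag?** Expedited reporting does, because the sponsor's decision rests on seriousness, causality and expectedness (Section 5.5.5). The serious TEAE tables do (both SAPs, Section 6.5.1). These do not:

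- the tables of ALT or AST > 3, > 5, > 8, > 10 and > 20 × ULN (both SAPs, Section 6.5.2.1);
- the summaries and listings of liver test elevations as an adverse event of special interest (both SAPs, Section 6.5.1);
- the LA-CRF, required for confirmed moderate and severe abnormalities (Appendix 12.4);
- the Liver Safety Monitoring Panel, which reviews cases meeting the withdrawal criteria (Section 10.2).

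**The case against.** The best reply is that the two sentences can both be obeyed. The Follow-up sentence does not say that cases with another cause are not SAEs, and the stop list says that the listed ones must be reported. A site that reports every case complies with both, and a site that omits one breaches an explicit instruction. On this view there is only a risk of misreading.

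This reading is possible, but it leaves the qualifier with no function, and no passage says that the stop list prevails. The qualifier comes first, in the instructions for follow-up, and the sponsor-contact sentence after it is also tied to possible attribution. A site could reasonably take it as a limit. The sponsor may also judge seriousness (Section 5.5.2) and keeps a list of events that it always treats as serious (Section 5.5.2.1). The content of that list is not shown, and it acts only on events that the site has reported as AEs.

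Two stronger readings are tempting but not supported:

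- **That the conditional sentence cannot work within the 24-hour reporting time.** Section 5.5.3 expects first SAE reports with little information and later revision. Before the work-up, no other cause has been established, so the sentence can be read as requiring the report.
- **That the Data Monitoring Committee would see too little liver harm.** Section 10.1 has it review safety data in general. Central laboratory alerts and the outputs listed under Step 6 continue regardless of the SAE flag. At most, SAE summaries would be affected.

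**Conclusion.** The inconsistency is real and lies within Appendix 12.4. Four laboratory criteria carry two SAE rules, and a severe case with another cause is treated differently under each. Sections 5.5.1.2, 5.5.2 and 6.1 together agree with the unconditional rule, through discontinuation. The effect is confined to SAE and expedited reporting and the serious TEAE tables, and it arises only if a site follows the conditional sentence. It is worth correcting because liver injury is a named important potential risk, serious liver events are likely to be few, and the correction is nearly free.

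No percentage should be attached to it. A reader might infer one from phase 2b, where 9 women had ALT or AST > 3 × ULN, 3 of them > 8 × ULN, and 5 discontinued for liver enzyme changes. Any loss worked out from these counts would rest wholly on an assumed share with another cause. The three cases > 8 × ULN were at 60 mg twice daily, 90 mg twice daily and 60 mg once daily (Section 1.4.2), all above the 30 and 45 mg once daily studied here. Section 1.5 reports no increased transaminases at 30 mg once daily, and the modelling in Section 2.2.2 predicts none > 3 × ULN at 30, 45 or 60 mg once daily. Nor do the phase 2b cases show that events are lost: they went to expert review and were judged probably drug-related.

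**What to change.** Reconcile the two sentences in Appendix 12.4 with Sections 5.5.1.2, 5.5.2 and 6.1 into one SAE reporting rule for the four listed criteria. One way is to remove the qualifier on cause for those criteria and to record any alternative cause in the causality assessment and on the LA-CRF, which already has a place for possible etiology.

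In the same edit:

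- align the sponsor-contact sentence with the 24-hour rule in Section 5.5.5, so that possible attribution is not read as a condition for contact about an SAE;
- state whether results that an investigator designates as severe outside the list fall under the rule. Removing the qualifier without this could make them automatic SAEs by accident.

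The stopping criteria need no change for this. The cost is a protocol wording change and at most a few additional SAE reports. No SAP analysis changes.
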